1. INTRODUCTION

This statistical analysis plan (SAP) describes the statistical analysis methods and data presentations to be used in tables, figures, and listings (TFLs) of the final analysis for Study GS-US-380-1961, which will be performed when all subjects have completed the study or prematurely discontinued from the study. This SAP is based on the study protocol amendment 2 dated 10 November 2016 and the electronic case report form (eCRF). The SAP will be finalized before data finalization for the final analysis. Any changes made after the finalization of the SAP will be documented in the clinical study report (CSR).

1.1. Study Objectives

The primary objective of this study is:

- To evaluate the efficacy of switching to a fixed dose combination (FDC) of bicitgravir (GS-9883; BIC; B) /emtricitabine (FTC; F) /tenofovir alafenamide (TAF) versus continuing on a regimen consisting of E/C/F/TAF, E/C/F/TDF, or ATV+RTV+FTC/TDF in virologically suppressed HIV-1 infected women as determined by the proportion of subjects with HIV-1 RNA ≥ 50 copies/mL at Week 48.

The secondary objective of this study is:

- To evaluate the safety and tolerability of the treatment groups through Week 48.

1.2. Study Design

Design Configuration and Subject Population

GS-US-380-1961 is a randomized, open-label, multicenter, active-controlled study to evaluate the safety and efficacy of switching to an FDC of B/F/TAF in HIV-1 infected women who are virologically suppressed (HIV-1 RNA < 50 copies/mL) on a regimen consisting of E/C/F/TAF, E/C/F/TDF, or ATV+RTV+FTC/TDF for ≥ 12 consecutive weeks prior to screening.

All subjects will be HIV-1 infected women drawn from pre-defined Gilead Sciences (Gilead) clinical studies and must be virologically suppressed. Women in Study GS-US-236-0128 who completed the Week 48 open-label extension (OLE) visit or any post Week 48 OLE visits, women in Study GS-US-292-0109 who completed the Week 96 visit or any post Week 96 visits, or women in Studies GS-US-292-0104 or GS-US-292-0111 who completed the Week 144 visit or any post Week 144 visits may be eligible to enroll in Study GS-US-380-1961.

Treatment Groups

Subjects who provide written consent and meet all eligibility criteria will be randomized in a 1:1 ratio to receive open-label medication as follows:

Treatment Group 1: FDC of BIC 50 mg/FTC 200 mg/TAF 25 mg (B/F/TAF) administered orally, once daily, without regard to food (approximately n = 235)

Treatment Group 2: Stay on baseline regimen (SBR), including E/C/F/TAF, E/C/F/TDF, or ATV+RTV+FTC/TDF administered orally, once daily, with food (approximately n = 235)

Key Eligibility Criteria

Medically stable HIV-1 infected women who meet the following criteria:

- Currently on a stable antiretroviral regimen consisting of E/C/F/TAF, E/C/F/TDF, or ATV+RTV+FTC/TDF continuously for ≥ 12 consecutive weeks preceding the screening visit
- Documented plasma HIV-1 RNA levels < 50 copies/mL for ≥ 12 weeks preceding the Screening visit. After reaching HIV-1 RNA < 50 copies/mL, single values of HIV-1 RNA ≥ 50 copies/mL followed by re-suppression to < 50 copies/mL is allowed
- HIV-1 RNA < 50 copies/mL at screening
- Estimated glomerular filtration rate (eGFR) ≥ 50 mL/min according to the Cockcroft-Gault (C-G) formula at the screening visit

Study Periods / Phases

Subjects will be treated for at least 48 weeks. At the Week 48 Visit, subjects in a country where B/F/TAF FDC is not available will be given the option to receive B/F/TAF FDC for an additional 48 weeks, or until the product becomes accessible to subjects through an access program, or until Gilead elects to discontinue the study in that country, whichever occurs first.

Subjects who complete the study through the Week 48 Visit and do not continue participation in the study will be required to return to the clinic 30 days after the Week 48 Visit for a 30 Day Follow-Up Visit.

Schedule of Assessments

After screening procedures, eligible subjects will be randomized 1:1 to Treatment Group 1 or Treatment Group 2 and treated for 48 weeks. Following the Screening and Day 1 visits, subjects will return for study visits at Weeks 4, 8, 12, and then every 12 weeks until the Week 48 visit.

For all eligible subjects, blood and urine will be collected at Day 1, Weeks 4, 8, 12, and then every 12 weeks through the Week 48 visit. Laboratory analyses (including hematology, chemistry, and urinalysis), HIV-1 RNA, CD4+ cell count, and complete or symptom-directed physical examinations will be performed at the Screening, Day 1, and all subsequent study visits.

Adverse events and concomitant medications will be assessed at each visit.

Pharmacokinetics

For all subjects on B/F/TAF (Treatment Group 1), a single anytime pre or post-dose PK blood sample will be collected at Weeks 8, 24, and 36.

For all subjects on B/F/TAF (Treatment Group 1), a trough PK blood sample will be obtained 20-28 hours following the last dose at Weeks 4 and 12. Following an observed dose, one PK blood sample will be collected between 1 and 4 hours post-dose.

The concentration of BIC may be summarized using descriptive statistics.

Randomization

Subjects will be randomized in a 1:1 ratio to 1 of 2 Treatment Groups (Treatment Group 1: Treatment Group 2). Randomization will be stratified by the prior treatment regimen group (ie, E/C/F/TAF, E/C/F/TDF, and ATV+RTV+FTC/TDF).

Site and/or Stratum Enrollment Limits

Approximately 57 study sites in North America, Dominican Republic, Thailand, Russia, and Uganda participated. There was no enrollment limit for individual sites.

Study Duration

The randomized phase of this study is 48 weeks in duration.

1.3. Sample Size and Power

A total of approximately 470 HIV-1 infected women, randomized in a 1:1 ratio to 2 treatment groups (approximately 235 subjects per treatment group), achieves at least 87% power to detect a non-inferiority margin of 4% difference in the percentage of subjects with HIV-1 RNA ≥ 50 copies/mL at Week 48 between the 2 treatment groups.

For sample size and power computation, it is assumed that both treatment groups have 2% of subjects with HIV-1 RNA ≥ 50 copies/mL at Week 48 (based on the historical Gilead Genvoya[®] [GEN; E/C/F/TAF] and Stribild[®] [STB; E/C/F/TDF] studies), that a non-inferiority margin is 4%, and that the significance level of the test is at a one-sided 0.025 level. Sample size and power calculations were made using the statistical software package nQuery Advisor (Version 6.0).

2. TYPE OF PLANNED ANALYSIS

2.1. Data Monitoring Committee Analysis

The Week 24 Independent Data Monitoring Committee (IDMC) analysis was conducted after all subjects enrolled completed their Week 24 visit of the study or prematurely discontinued the study drug. The purpose of this interim analysis was to provide the IDMC with a statistical report for review. More details are documented in the IDMC charter.

Gilead does not have a prior intent to ask the IDMC to review Week 48 result or to consider early termination of the study even if there is early evidence of favorable efficacy for B/F/TAF.

2.2. Week 48 Interim Analysis

The Week 48 interim analysis was conducted after all subjects either completed their Week 48 visit or prematurely discontinued from the study drug.

2.3. Final Analysis

The final statistical analysis will be conducted after all subjects either complete the study or prematurely discontinue from the study.

This SAP describes the analysis plan for the final analysis, which will only include the all B/F/TAF analysis: safety and efficacy assessments for B/F/TAF only, not for other study drugs.

3. GENERAL CONSIDERATIONS FOR DATA ANALYSES

The final analysis will include only the all B/F/TAF analysis in tables and figures, unless specified otherwise. The analysis for the randomized phase data exposed to SBR group was included in the Week 48 interim analysis and will not be repeated in this final analysis. However, data collected from the entire study will be included in data listings.

Analysis results will be presented using descriptive statistics. For categorical variables, the number and percentage of subjects in each category will be presented; for continuous variables, the number of subjects (n), mean, standard deviation (SD) or standard error (SE), median, first quartile (Q1), third quartile (Q3), minimum, and maximum will be presented.

By-subject listings will be presented for all subjects in the All Randomized Analysis Set unless otherwise specified, and sorted by subject ID number, visit date, and time (if applicable). Data collected on log forms, such as AEs, will be presented in chronological order within a subject. The actual treatment group will be used in the listings.

In general, age (in years) on the date of the first dose of study drug will be used for analyses and presentation in listings. For randomized but never dosed subjects in data listings, age on the date of randomization will be used. If only birth year is collected on the eCRF, "01 January" will be used for the unknown birth day and month for the purpose of age calculation, similarly, if only birth year and month are collected on the eCRF, "01" will be used for the unknown birth day for the purpose of age calculation.

3.1. Analysis Sets

Analysis sets define the subjects to be included in an analysis. Analysis sets and their definitions are provided in this section. Subjects included in each analysis set will be determined before data finalization. The analysis set will be included as a subtitle of each table, figure, and listing. A summary of the number and percentage of subjects in each analysis set will be provided by treatment group and in total.

3.1.1. All Randomized Analysis Set

The **All Randomized Analysis Set** will include all subjects who were randomized into the study. This is the primary analysis set for by-subject listings.

3.1.2. All B/F/TAF Analysis Set

The **All B/F/TAF Analysis Set** includes all subjects who (1) were randomized to B/F/TAF and have received at least 1 dose of B/F/TAF during the randomized phase or (2) have received at least 1 dose of B/F/TAF during the extension phase. This is the primary analysis set for all B/F/TAF efficacy and safety analyses.

3.2. Subject Grouping

For the all B/F/TAF analysis including extension phase, subjects will be grouped into the following groups:

- B/F/TAF group: This group includes all subjects who were randomized to B/F/TAF in the randomized phase of this study. All data from both the randomized and extension phases (if applicable) will be included.
- Stay on Baseline Regimen (SBR) to B/F/TAF group: This group includes all subjects who were randomized to continuing pre-existing regimen in the randomized phase of this study, and who then switched to B/F/TAF in the extension phase. Only data collected on and after the extension phase first dose date of B/F/TAF will be included, except that data collected **on or prior to** the extension phase first dose date of B/F/TAF will be used to derive the baseline value for the all B/F/TAF analysis.
- All B/F/TAF group: This group includes all subjects who are in the All B/F/TAF Analysis Set, which combines the two groups above.

3.3. Strata and Covariates

There is no stratification for analysis.

3.4. Examination of Subject Subgroups

In order to explore the effect of switching from TDF to TAF on renal functions,, subgroup analysis by prior treatment regimen (ie, TDF-containing regimen versus non-TDF containing regimen) will be performed for the following endpoints:

- Urine retinal binding protein (RBP) to creatinine ratio
- beta-2 microglobulin to creatinine ratio
- Urine albumin to creatinine ratio (UACR)

3.5. Multiple Comparisons

Multiple comparisons and alpha adjustment were applied for the primary endpoint analysis conducted at Week 48. No alpha level adjustment is applied in the final analysis.

3.6. Missing Data and Outliers

3.6.1. Missing Data

A missing datum for a given study analysis window may be due to any of the following reasons:

- A visit occurring in the window but data were not collected or were unusable
- A visit not occurring in the window
- A subject prematurely discontinuing from the study before reaching the window

In general, values for missing data will not be imputed, unless methods for handling missing data are specified.

For missing last dosing date of study drug, imputation rules are described in Section 3.8.1. The handling of missing or incomplete dates for AE onset is described in Section 7.1.5.2, and for concomitant non-antiretroviral (ARV) medications in Section 7.4.2.

3.6.2. Outliers

Outliers will be identified during the data management and data analysis process, but no sensitivity analyses will be done to evaluate the impact of outliers on efficacy or safety outcomes, unless specified otherwise. All data will be included in the analyses.

3.7. Data Handling Conventions and Transformations

Laboratory data that are continuous in nature but are less than the lower limit of quantitation or above the upper limit of quantitation will be imputed as follows except for urine creatinine:

- A value that is 1 unit less than the limit of quantitation will be used for calculation of descriptive statistics if the datum is reported in the form of “< x” (where x is considered the limit of quantitation). For example, if the values are reported as < 50 and < 5.0, values of 49 and 4.9, respectively, will be used for calculation of summary statistics. An exception to this rule is any value reported as < 1 or < 0.1, etc. For values reported as < 1 or < 0.1, a value of 0.9 or 0.09, respectively, will be used for calculation of summary statistics.
- A value that is 1 unit above the limit of quantitation will be used for calculation of descriptive statistics if the datum is reported in the form of “> x” (where x is considered the limit of quantitation). Values with decimal points will follow the same logic as above.
- The limit of quantitation will be used for calculation of descriptive statistics if the datum is reported in the form of “≤ x” or “≥ x” (where x is considered the limit of quantitation).

For urine creatinine, a value of “< 1” is handled as a missing value in its summary and the calculation of related ratios.

Logarithm (base 10) transformation will be applied to HIV-1 RNA data for efficacy analysis. HIV-1 RNA results of ‘No HIV-1 RNA detected’ and “<20 cp/mL HIV-1 RNA Detected” will be imputed as 19 copies/mL for analysis purpose.

3.8. Analysis Windows

For subjects who were randomized to SBR and discontinued study drug in the randomized phase (ie, subjects who were in the All Randomized Analysis Set, but not in the All B/F/TAF Analysis Set), the definition and derivation of the necessary variables presented in the data listings (eg, first dose date, last dose date, study date, etc.) can be found in [Appendix 4](#).

For the all B/F/TAF analysis that only evaluates the efficacy and safety of B/F/TAF, the study drug mentioned in the following only refers to B/F/TAF.

3.8.1. Definitions

Study Day 1 is defined as the day when the first dose of B/F/TAF (either in the randomized phase or extension phase) was taken. For subjects randomized to the B/F/TAF group, the first dose date is the same as the randomized phase first dose date. For subjects randomized to the SBR group, the first dose date is defined as the earliest nonmissing start date of B/F/TAF recorded on the Study Drug Administration eCRF.

Study Days are calculated relative to Study Day 1 for the all B/F/TAF analysis. For events that occur on or after the Study Day 1 date, study days are calculated as (visit date minus date of the first dose plus 1). For events that occur prior to Study Day 1, study days are calculated as (visit date minus date of the first dose).

Last Dose Date is defined as the maximum, nonmissing end date of B/F/TAF, recorded on the Study Drug Administration eCRF form with “Study Drug Permanently Discontinued” box checked for subjects who prematurely discontinued study drug or who completed study drug according to the Study Drug Completion eCRF.

If the date of last dose is missing (eg, due to lost to follow-up) for subjects who prematurely discontinued study drug, the maximum of nonmissing study drug start dates and end dates, the clinical visit dates, and the laboratory visit dates excluding the date of 30-day follow-up visit will be used to impute the last dose date.

Last Study Date is the maximum of nonmissing study drug start dates and end dates, the clinic visit dates, and the laboratory visit dates, including the 30-day follow-up visit date for subjects who prematurely discontinued or completed the study according to the Study Completion eCRF.

Baseline value is defined as the last nonmissing value obtained on or prior to the Study Day 1 for all assessments.

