### 6.4. Treatment Assessments (Weeks 4-48)

The following evaluations are to be completed at the end of Weeks 4, 8, 12, 24, 36, and 48 unless otherwise specified.

Study visits are to be completed within  $\pm$  2 days of the protocol-specified visit date based on the Day 1 visit through Week 12 and completed within  $\pm$  6 days at Week 24 and Week 36, unless otherwise specified. The visit window at Week 48 will be  $\pm$  6 weeks of the protocol-specified visit date, and these clinical visit windows coincide with the Week 48 statistical analysis window for HIV-1 RNA.

Regularly scheduled evaluations will be made on all subjects whether or not they continue to receive study drug.

- Review of AEs and changes in concomitant medications
- Complete physical examination (**Weeks 24 and 48**) (urogenital/anorectal exams will be performed at the discretion of the Investigator) or symptom-directed physical examination as needed
- Vital signs measurement (blood pressure, pulse, respiration rate, and temperature), including weight
- 12-lead ECG performed supine (**Weeks 24 and 48**)
- Urine collection for the following laboratory procedures:
  - Urinalysis
  - Urine albumin, urine creatinine, urine protein, retinol binding protein and beta-2 microglobulin (**Weeks 24 and 48**)
  - Urine pregnancy test (females of childbearing potential only); positive urine pregnancy tests will be confirmed with a serum test. If the test is positive, subjects on GS-9883/F/TAF will be discontinued.
  - Urine storage sample for possible additional clinical testing

- Blood sample collection for the following laboratory analyses:
  - Chemistry profile: alkaline phosphatase, AST, ALT, GGT, total bilirubin, direct and indirect bilirubin, total protein, albumin, bicarbonate, BUN, calcium, chloride, creatinine, glucose, phosphorus, magnesium, potassium, sodium, uric acid, and amylase (reflex lipase testing is performed in subjects with total amylase  $> 1.5 \times$  ULN). At Weeks 12, 24 and 48, analyses of glucose will be done as part of the fasting metabolic assessments and not as part of the chemistry profile. At Weeks 24 and 48, TSH will also be analyzed.

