## **6.6. Post-Treatment Assessments**

### **6.6.1. Early Study Drugs Discontinuation (ESDD) Assessments**

If the subject discontinues study drug prior to the Week 48 Visit, the subject will be asked to return to the clinic within 72 hours of stopping study drug for the Early Study Drugs Discontinuation Visit. The subject will be asked to continue attending the scheduled study visits through the Week 48 Visit.

**At the Early Study Drugs Discontinuation Visit, any evaluations showing abnormal results indicating that there is a possible or probable causal relationship with the study drug, will be repeated weekly (or as often as deemed prudent by the Investigator) until the abnormality is resolved, returns to baseline, or is otherwise explained.**

The following evaluations are to be completed at the Early Study Drugs Discontinuation Visit:

- Review of AEs and changes in concomitant medications
- Complete physical examination (urogenital/anorectal exams will be performed at the discretion of the Investigator)
- 12-lead ECG performed supine
- Vital signs measurement (blood pressure, pulse, respiration rate, and temperature), including weight
- Urine collection for the following laboratory procedures:
  - Urinalysis
  - Urine pregnancy test (women of childbearing potential only); positive urine pregnancy tests will be confirmed with a serum test.
  - Urine storage sample for possible additional clinical testing
- Blood sample collection for the following laboratory analyses:
  - Chemistry profile: alkaline phosphatase, AST, ALT, GGT, total bilirubin, direct and indirect bilirubin, total protein, albumin, bicarbonate, BUN, calcium, chloride, creatinine, glucose, phosphorus, magnesium, potassium, sodium, uric acid, and amylase (reflex lipase testing is performed in subjects with total amylase  $> 1.5 \times$  ULN), and TSH
  - Estimated glomerular filtration rate according to the Cockcroft-Gault formula
  - Hematology profile: complete blood count (CBC) with differential and platelet count
  - Plasma HIV-1 RNA
  - CD4+ cell count
  - Plasma storage samples for safety, virology, or PK testing
  - Plasma HBV DNA (for subjects who meet the definition of HBV infection)
  - HIV-1 genotype/phenotype testing for subjects with virologic failure
- Drug accountability

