7.4. Prior and Concomitant Medications

7.4.1. Antiretroviral Medications

Any nonstudy ARV medications used prior to, during, or after the study (if collected) are all recorded on the ARV eCRF. All ARV medications recorded on the ARV eCRF will be coded using the Gilead-modified World Health Organization (WHO) Drug Dictionary for ARV medication. The WHO preferred name and drug code will be attached to the clinical database. All ARV medications recorded on the ARV eCRF will be listed. No inferential statistics will be provided.

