 - e) If the DOB and Day 1 have the month in common and the birthday is later in the month than the date of Study Day 1, then subtract one from the AGE result above.

- 3) In disposition table, the reasons for premature discontinuation are displayed in the order as they appear on the eCRF.
- 4) Body mass index (BMI) and Body Surface Area (BSA)

BMI and BSA will be calculated as follows:

- $BMI = (\text{weight [kg]} / (\text{height [meters]}^2))$
- $BSA (m^2) = \text{SQRT}([\text{Height(cm)} \times \text{Weight(kg)}] / 3600)$

All B/F/TAF baseline height and weight of the study will be used for this calculation.

- 5) Last Dose Date of B/F/TAF and Last Study Date

Last Dose Date in ADSL was defined in Section 3.8.1.

For subjects with a partial last dosing date of B/F/TAF (ie, month and year of last dose are known), the minimum of {(death date, if available), (the latest of the dispensing dates of B/F/TAF bottles, B/F/TAF start dates and end dates (based on EX dataset), and the imputed last dose date [day imputed as 15])} will be used as the final imputed last dose date. However if dispensing date's month is after last dose date's month, data query is needed.

Last Study Date is the latest of the study drug start dates and end dates, the clinic visit dates, and the laboratory visit dates, including the 30-day follow-up visit date, for subjects who prematurely discontinued study or who completed study according to the Study Completion eCRF. If study drug start dates or end dates is partially missing (ie, only year and month are known), the day will be imputed as 15 for the purpose of this analysis.

- 6) Treatment Group Presented in the Listings

In data listings, the treatment group will be presented as follows:

B/F/TAF: subjects who were randomized into B/F/TAF group in the randomized phase, either entered into the extension phase or not;

SBR: subjects who were randomized into SBR group in the randomized phase and did not enter into the extension phase of B/F/TAF;

SBR to B/F/TAF: subjects who were randomized into SBR group in the randomized phase and entered into the extension phase of B/F/TAF.

7) Toxicity Grades:

- i) For toxicity grade summaries, include all postbaseline graded results up to 30 days after the last dose of B/F/TAF, not just those used in by-visit summaries.

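### The SAP 3.8.1 rule for a wholly missing last B/F/TAF dose date has no cut-off at discontinuation, so a woman who stops before Week 48 and keeps attending is given an off-drug visit as her last dose

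*SAP*

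**What the plan says.** SAP 3.8.1 normally takes the last dose date from the Study Drug Administration eCRF, as the latest B/F/TAF end date on a record marked as permanent discontinuation. The fallback begins: "If the date of last dose is missing (eg, due to lost to follow-up) for subjects who prematurely discontinued study drug". The imputed date is then a maximum that covers drug start and end dates together with visits: "the clinical visit dates, and the laboratory visit dates excluding the date of 30-day follow-up visit will be used to impute the last dose date". The 30-day follow-up visit is the only visit left out.

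The protocol plans visits after discontinuation. Section 6.4 states: "Regularly scheduled evaluations will be made on all subjects whether or not they continue to receive study drug". Section 6.6.1 says that, after stopping before Week 48, "the subject will be asked to return to the clinic within 72 hours of stopping study drug" for the ESDD visit, and then: "The subject will be asked to continue attending the scheduled study visits through the Week 48 Visit". Section 6.6.2 waives the 30-day follow-up visit for a woman who attends at least one visit after the ESDD visit. The notes to Figure 6-1 and Appendix 6 both foresee women staying in the study on a new ARV regimen.

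SAP Appendix 5 item 5 has a separate rule that opens "For subjects with a partial last dosing date of B/F/TAF (ie, month and year of last dose are known"). It uses dispensing dates, drug dates and a day set to 15, capped by the death date. It uses no clinic or laboratory visit dates.

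**The concern.** The fallback treats the last contact as the last dose. For a woman lost to follow-up the two may be close. For a woman who stopped drug and stayed in the study they can be months apart, and nothing in 3.8.1 tells the programmer to stop at discontinuation. Loss to follow-up is given only as an example, so the rule as written covers both women.

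The last dose date feeds much of the final analysis:

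- duration of exposure (SAP 4.2.1);
- the on-treatment cut for CD4 (6.2.1) and the last on-treatment urine albumin to creatinine ratio (7.2.5.3), both at last dose plus 1 day;
- the windows for laboratory abnormalities (7.2.2), liver tests (7.2.4) and treatment-emergent deaths (7.1.6), all at last dose plus 30 days;
- the classification of adverse events with incomplete onset dates (7.1.5.2);
- concomitant medications (7.4.2).

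Kaplan-Meier time to discontinuation (4.2.1) is probably affected too, although the SAP does not define its event date. For an affected woman, results obtained off drug, possibly on another regimen, would be labelled B/F/TAF, and her discontinuation would look later than it was.

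**Working it through.** The plan gives no figure for this point, so there is none to reproduce. The check has two parts.

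**1. What the rule returns for each kind of woman**

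| Situation | Date from the SAP rule | On drug at that date? |
|---|---|---|
| Last dose date recorded | eCRF end date | Yes |
| Month and year known | Appendix 5 item 5; no visit dates | Approximately: day 15 alone is off by at most 16 days, though a later dispensing or drug date can move it |
| Wholly missing, lost to follow-up | Last contact | Plausibly |
| Wholly missing, stops in the extension phase | Last contact; the only later visit described is the 30-day follow-up, which is excluded | Plausibly |
| Wholly missing, stops before Week 48, stays in the study | Last scheduled visit attended | No |

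Only the last row fails.

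**2. Size for one affected woman**

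Inputs:
- Exposure = last dose date − first dose date + 1, in weeks (SAP 4.2.1). With first dose on Day 1 and last dose on Day *s*, this is *s*/7.
- Nominal Week 48 visit: Day 336. Upper limit of the Week 48 window: Day 378 (Protocol 8.5.1.1; SAP Table 3-1).
- Stop day *s*: assumed, since the documents give none.

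Overstatement = (336 − *s*)/7 or (378 − *s*)/7 weeks.

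| Stop day | True weeks | Imputed, Day 336 | Excess | Imputed, Day 378 | Excess |
|---|---|---|---|---|---|
| 28 | 4 | 48 | 44 | 54 | 50 |
| 56 | 8 | 48 | 40 | 54 | 46 |
| 84 | 12 | 48 | 36 | 54 | 42 |
| 168 | 24 | 48 | 24 | 54 | 30 |
| 252 | 36 | 48 | 12 | 54 | 18 |

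For example, a stop on Day 56 gives 336 − 56 = 280 days, or 40 weeks.

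**Effect on the group mean.** Take the planned 235 women randomised to B/F/TAF and the largest excess (44 to 50 weeks each, from a Day 28 stop). The mean exposure shifts by *k* × 44/235 to *k* × 50/235 weeks for *k* affected women:
- *k* = 1: 0.19 to 0.21 weeks
- *k* = 2: 0.37 to 0.43 weeks
- *k* = 5: 0.94 to 1.06 weeks

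**With visits limited to the ESDD visit.** That visit is due within 72 hours of stopping, so the excess is at most about 3 days when it takes place on time.

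**The case against.** The strongest objection is that the conditions rarely coincide. The woman must have a wholly missing date, have stopped before Week 48, and have stayed in the study. Such a woman is asked to attend an ESDD visit with drug accountability. Drug start and end dates are required source data (Protocol 9.1.5), and discrepancies are queried (9.1.6). She is the woman least likely to lack a date. This stands, and it makes the point a small one. It does not make the rule right for the case that it covers.

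Three stronger readings are tempting, and the documents do not support them.

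- *The SAP contains two conflicting rules.* Appendix 5 item 5 is triggered by a partial date and 3.8.1 by a missing one. They differ in method but cover different cases. What is missing is a sentence saying which applies when.
- *Every safety output would credit another regimen's data to B/F/TAF.* The main treatment-emergent definition (SAP 7.1.5.1) is tied to permanent discontinuation of B/F/TAF, and routine collection of adverse events ends 30 days after the last dose (Protocol 7.3.1). Later non-serious events are therefore not planned to be collected. Serious events, which are reported throughout the study (7.3.2), are the main ones that could be drawn in.
- *The non-inferiority result is affected.* The snapshot algorithm does use on-treatment HIV-1 RNA, but this SAP states that the Week 48 analysis was already done and is not repeated. The documents do not show how that analysis imputed a missing date.

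The reach is also limited by group. Women in the SBR to B/F/TAF group take B/F/TAF only in the extension phase, so continued attendance to Week 48 cannot affect them. Protocol 6.10 encourages retention in general but sets no visit schedule after an extension-phase stop.

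**Conclusion.** The point holds in a narrow form. As written, SAP 3.8.1 returns an off-drug date for a woman randomised to B/F/TAF who stops before Week 48, continues attending and has a wholly missing last dose date. The protocol deliberately creates that attendance pattern, and the one exclusion in the rule does not help her. Her exposure is overstated by 12 to 50 weeks in the scenarios shown, which rest on assumed stop days and on attendance through Week 48. The CD4, albumin-ratio, laboratory, liver-test, death, incomplete-date adverse event and concomitant-medication derivations move with it, and the Kaplan-Meier analysis probably does.

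The documents do not state how many women meet all the conditions, and the number may be zero. At the group level one such woman shifts mean exposure by about 0.2 weeks at most. The effect is shown only for the descriptive final all-B/F/TAF analysis. The correction is worth making because it costs almost nothing, not because a conclusion of the trial depends on it.

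**What to change.** Amend SAP 3.8.1 as follows.

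1. State that the rule applies only when the last dose date is wholly missing, and that Appendix 5 item 5 handles partial dates.
2. Use clinic and laboratory visits only up to and including the ESDD visit.
3. Cap the imputed date at the day before the first non-study ARV that was started after the first B/F/TAF dose, and never let it fall before the first B/F/TAF dose date.

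The restriction to ARVs started after the first dose is essential. SAP 7.4.1 says: "Any nonstudy ARV medications used prior to, during, or after the study (if collected) are all recorded on the ARV eCRF". A cap at the earliest ARV start on that form could put the last dose before the first and give negative exposure.

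A woman who misses the ESDD visit but attends later ones needs a stated fallback. The dispensing and drug dates already used in Appendix 5 item 5 would serve. A death-date cap like the one there is optional and adds little, since visits do not follow death.

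The cost is one or two sentences and a line or two of code. The ESDD dates and ARV records are already planned for collection. If the SAP is treated as final, its introduction already provides for documenting later changes in the clinical study report. That report should also give the number of last dose dates imputed under each rule.
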